16.8.6 Other Time to Event Efficacy Endpoints

Other time-to-event outcomes (all-cause discontinuation, and remission duration) further characterize this multi-component disorder. Time to event is a more sensitive measure than an assessment at a fixed time. Time to such events will be displayed using a Kaplan-Meier lifetable, with the treatment groups compared using two-sided unstratified log rank tests (secondary) and a proportional hazard model (primary) to include the above cited baseline covariates.

Treatment Failure will be centrally judged blind in real time by the study physician using baseline measures of depression and suicidality as a guide. Treatment failure is defined above.

16.8.7 Secondary Efficacy Endpoints

All of the instruments used to measure SSIB or depression constitute serial continuous and ordinal outcomes that will be analyzed using MMRM with LOCF, which accounts for missing data and early discontinuations. Results will be presented separately for each treatment group.

The models will include treatment group, study visit, the interaction between study visit and treatment group, the randomization baseline of the variable being analyzed, and the three baseline stratification factors as fixed effects. The reason for missing data will be evaluated as a condition of MMRM analysis.

16.8.8 Other Endpoints of Interest

The following additional endpoints will be recorded and analyzed by treatment group for both study phases:

- Dose per treatment group
- Suicide rates
- Proportion of participants who are treated with new SSRIs or have increased SSRI dosages
- Proportion of participants who discontinue SSRIs or have reduced SSRI dosages
- Efficacy for each BPI factor.

Dose per treatment group will be displayed graphically over time per study treatment group. The percent decreasing and increasing over time relative to starting dose will be displayed per study treatment group.

Time to all-cause study discontinuation and time to discharge will be displayed using a Kaplan-Meier lifetable.

The following three measures will be separately evaluated using a two-sided Fisher Exact test to compare treatments:

- the need to implement a new treatment plan.
- an increase in suicidal ideation (a score of ≥ 4 on the C-SSRS, emergent suicidality requiring hospitalization).
- an increase in depressive symptoms (a score increase of ≥ 5 for two consecutive visits on the MADRS total score).

The incidence of hospitalization and ER visits will be evaluated using a Wilcoxon Rank Sum test to compare each study treatment group.

The proportions of participants discontinuing SSRIs or reducing SSRI dosages will be displayed graphically over time per study treatment group. The percent discontinuing SSRIs and reducing SSRI dosages relative to starting dose will be displayed per study treatment group.

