## **17.2 Safety Assessments**

- Change from baseline to endpoint (Day 42) in C-SSRS score
- Change from baseline to endpoint (Day 14) in C-SSRS score
- Mean change in BARS through Day 42 to assess akathisia
- Rates of discontinuation between the arms

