#### 19.4 Estimand Structure

Analyses will be conducted in accordance with ICH E9 (R1) analysis principles as summarized below.

Primary scientific question of interest	The primary study hypothesis is that treatment with NRX-101 is superior to lurasidone in improving symptoms of depression as measured by the MADRS over 6 weeks of treatment. The null hypothesis for the primary endpoint is the mean change from baseline of MADRS-10 for NRX-101 is the same as lurasidone while the alternative hypothesis is that the mean change from baseline of MADRS-10 is larger than the mean change from baseline of MADRS-10 for lurasidone. Baseline is defined as MADRS-10 score at Visit 2 (randomization).
Target population	The mITT population will be the primary analysis population. The mITT population is defined through appropriate inclusion/exclusion criteria as specified in the protocol and blinded BDRM decisions.
Treatment of interest	NRX-101
Outcome Variables	MADRS-10 (and C-SSRS) will be recorded as audio files and reviewed by central master-raters with any non-congruent subject-visits from any site with >10% non-congruent scores sent to a qualified independent adjudicator to be considered as the subject-visit primary study endpoint.
Summary Measure	The contrast-estimated MADRS-10 Week 6 MMRM will use all post-randomization data with LOCF in the mITT population excluding all outcomes after BDRM-approved exclusions. The model will include treatment and the following four baseline covariates in addition to baseline MADRS-10: (1) sex, (2) mood stabilizer use, (3) anti-psychotic use, and (4) evidence of suicide event in their lifetime. The model will include treatment group, study visit, the interaction between study visit and treatment group, baseline MADRS-10, and the four baseline covariates as fixed effects. An unstructured error structure will be assumed.
Intercurrent Events	A BDRM will adjudicate all intercurrent events which may redact outcomes after disqualifying events; these intercurrent events may represent major protocol deviations.

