### **20.3 Secondary Efficacy Endpoints**

All of the instruments used to measure SSIB or depression constitute serial continuous and ordinal outcomes that will be analyzed using MMRM with LOCF, which accounts for missing data and early discontinuations. Results will be presented separately for each treatment group.

The models will include treatment group, study visit, the interaction between study visit and treatment group, the randomization baseline of the variable being analyzed, and the four baseline stratification factors as fixed effects. The reason for missing data will be evaluated as a condition of MMRM analysis.

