### **20.4 Other Efficacy Endpoints**

The following additional endpoints will be recorded and analyzed by treatment group for both study phases:

- Dose per treatment group
- Suicide rates
- Proportion of participants who are treated with new SSRIs or have increased SSRI dosages
- Proportion of participants who discontinue SSRIs or have reduced SSRI dosages
- Efficacy for each BPRS factor.

Dose per treatment group will be displayed graphically over time per study treatment group. The percent decreasing and increasing over time relative to starting dose will be displayed per study treatment group.

Time to all-cause study dropout will be displayed using a Kaplan-Meier lifetable.

The following three measures will be separately evaluated using a two-sided Fisher Exact test to compare treatments:

- the need to implement a new treatment plan.
- an increase in suicidal ideation (a score of  $\geq 4$  on the C-SSRS, emergent suicidality requiring hospitalization).
- an increase in depressive symptoms (a score increase of  $\geq 5$  from the previous on-study visit for two consecutive visits on the MADRS total score).

The number of hospitalization and ER visits per subject will be evaluated using a Wilcoxon Rank Sum test to compare each study treatment group.

The proportions of participants discontinuing SSRIs or reducing SSRI dosages will be displayed graphically over time per study treatment group. The percent discontinuing SSRIs and reducing SSRI dosages relative to starting dose will be displayed per study treatment group.

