## 20.5 Safety Endpoints

Adverse events will be classified by MedDRA. For each study treatment, safety data will be collected and analyzed while on treatment or until treatment-emergent adverse events are resolved. The type, incidence, timing (onset, duration), relationship, and severity of AEs will be reported for treatment-emergent and SAEs. Reasons for withdrawal due to AEs will also be reported. Narratives will be written for every AE classified as serious or associated with attempted suicide or death.

Safety and tolerability will be assessed using two-sided Fisher Exact tests to compare overall adverse event incidence for NRX-101 vs. lurasidone. Mean changes from randomization baseline will be displayed for each serum chemistry and hematology parameter as well as the shift; unpaired t-tests will be used to compare treatments. In addition, paired t-tests will be performed for the changes from randomization baseline for each study treatment group.

C-SSRS will also be considered as a safety endpoint but will be analyzed as a McNemar paired comparison test within treatment groups and as a Jonchkeere-Terpstra test to compare treatment groups.

Vital signs and ECGs (means and mean changes from baseline will also be evaluated within treatment groups using paired t-tests and between study treatment groups using unpaired t-tests. Percent with abnormal vital signs, heart rate, QRS duration, PR interval, RR interval, QT, and QTcF will be reported. McNemar paired comparison tests will be performed within study treatment groups for the abnormal discordant percent while two-sided Fisher Exact tests will be performed to compare incidences between treatment groups.

Blood draws for chemistries and hematologies will be evaluated within and between study treatment groups. Abnormality rates will be presented relative to established site-specific normal ranges and whether or not the abnormality is clinically significant. McNemar paired comparison tests will be performed within study treatment groups for the abnormal percents while two-sided Fisher Exact tests will be performed to compare incidences between treatment groups.

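### The Fisher measure of increased suicidal ideation sets an absolute C-SSRS score of 4 or more without a reference visit, so on one permitted reading a patient unchanged at 4 counts as an increase

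*Protocol*

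**What the plan says.** SAP 20.4 introduces a list of three measures: "The following three measures will be separately evaluated using a two-sided Fisher Exact test to compare treatments". Protocol 16.8.8 has the same list. The second item is "an increase in suicidal ideation (a score of ≥ 4 on the C-SSRS, emergent suicidality requiring hospitalization" in the protocol, and the SAP keeps that definition ("on the C-SSRS, emergent suicidality requiring hospitalization"). Neither document gives a baseline, a prior visit or a change score for it, and only a comma separates the score from the hospitalization phrase.

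The third item, on MADRS worsening, was amended. The SAP adds a reference, "from the previous on-study visit for two consecutive visits on the MADRS total score", that protocol 16.8.8 lacks. The C-SSRS item received no such addition.

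Patients can start at the threshold. The SAP synopsis describes entry at a C-SSRS rating of 3 or 4, and inclusion criterion 10 accepts a positive answer on item 3, item 4 or both, with item 5 negative. Protocol 9.1.2 requires C-SSRS eligibility still to be met on Day 1. Ratings after Screening cover the time since the last visit (SAP 12.1.1).

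On baseline, SAP 19.4 says "Baseline is defined as MADRS-10 score at Visit 2 (randomization") for MADRS only. SAP 20.3 uses "the randomization baseline of the variable being analyzed" in the models for instruments that measure suicidality or depression. Table 1 labels the Day 1 column as baseline and schedules the C-SSRS there.

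**The concern.** A measure named as an increase should count patients who got worse. With an absolute cut-off at a level where patients may already stand, it can also count patients who have not changed. The comparison would then pool worsening with non-improvement under one label.

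Two things could follow. A between-arm difference in persistence at 4 could be reported as a difference in worsening. Or a real difference in worsening could be diluted by unchanged patients counted in both arms. The same C-SSRS data feed other analyses: SAP 17.2 lists "Change from baseline to endpoint (Day 42) in C-SSRS score", and SAP 20.5 compares arms "as a Jonchkeere-Terpstra test to compare treatment groups". A reader could see those results disagree with the Fisher result and have no explanation in the plan.

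**Working it through.** The documents state no rate, power or sample size for this measure, so there is no figure of the plan's to reproduce.

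**Step 1: which score pairs are misclassified.** Compare the literal rule (post-baseline score of 4 or more, hospitalization as an alternative) with a true rise (post-baseline score above Day 1 score).

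| Day 1 | Post-baseline | Literal rule | True rise |
|---|---|---|---|
| 3 | 2 | no | no |
| 3 | 3 | no | no |
| 3 | 4 | yes | yes |
| 3 | 5 | yes | yes |
| 4 | 2 | no | no |
| 4 | 3 | no | no |
| 4 | 4 | **yes** | **no** |
| 4 | 5 | yes | yes |

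One of the eight pairs disagrees: 4 to 4.

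**Step 2: what the missing connective does.** If the score and hospitalization are both required, an unchanged outpatient at 4 is not counted. That reading has its own gap: an outpatient who rises from 3 to 4 is not counted either. If they are alternatives, the 4-to-4 patient is counted.

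**Step 3: dilution of a true signal (illustration; every rate assumed).** Inputs: 37 per arm (protocol 16.6.2) and two-sided alpha 0.05 (SAP 19.3). Let r be the true-increase rate, s the share entering at 4, and u the probability that a patient who entered at 4 and had no true increase scores 4 again at some visit. Take r as the same whatever the entry score.

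Counted rate = r + (1 − r) × s × u.

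With r = 0.05 (NRX-101) and 0.30 (lurasidone), and u = 0.60:

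- Only true increases counted: 0.05 vs 0.30, Fisher power 0.78.
- s = 0.25: 0.193 vs 0.405, power 0.43.
- s = 0.50: 0.05 + 0.95 × 0.30 = 0.335 vs 0.30 + 0.70 × 0.30 = 0.510, power 0.24.
- s = 0.75: 0.478 vs 0.615, power 0.15.

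At s = 0.50 the patients counted without any increase number 37 × 0.95 × 0.30 = 10.5 on NRX-101 and 37 × 0.70 × 0.30 = 7.8 on lurasidone.

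**Step 4: persistence reported as worsening (illustration; nobody worsens).** Counted rate = s × persistence at 4, for s = 0.25, 0.50 and 0.75.

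- Persistence 40% in both arms: 74 × s × 0.40 = 7.4, 14.8 and 22.2 patients carry the increase label. The test gives p < 0.05 in either direction in only about 1% to 3% of trials.
- Persistence 30% on NRX-101 vs 50% on lurasidone: p < 0.05 favouring NRX-101 in 4%, 12% and 22% of trials.
- Persistence 20% vs 60%: 16%, 49% and 76%.

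With the arms exchanged, the same percentages favour lurasidone. Under a rule that requires a rise above the patient's own score, the counted rate in Step 4 is zero in both arms.

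**The case against.** The strongest reply is that the text can be read without any miscount. The parenthesis qualifies the phrase before it, so the measure may mean an increase that reaches 4, and the word emergent also suggests something new. On that reading, or on the joint reading, a 4-to-4 patient is not counted. This stands: the miscount depends on taking the parts as alternatives and applying the threshold literally. It does not settle the matter, because the plan does not choose among the readings and the choice changes who is an event.

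A second reply is that a baseline can be inferred. Table 1 labels Day 1 as baseline, and SAP 20.3 uses the randomization baseline for suicidality instruments. This also stands, and it tells against any claim that the documents leave the baseline visit wholly open. What is missing is the application of that baseline to this measure.

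A third reply is that the closely related judgement of treatment failure is made centrally and blind, with baseline suicidality as a guide (protocol 16.8.6, SAP 20.2). That suggests what the sponsor intends, but it governs treatment failure and not this Fisher comparison.

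A reader might infer from the 76% figure that the test is biased or yields false positives. It does not show that. With equal persistence the test is, if anything, conservative; the larger percentages reflect detection of an assumed real difference, under the wrong name.

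**Conclusion.** The point holds as a minor one. On a reading that the text permits, the stated rule counts one score combination, 4 to 4, as an increase when nothing has changed. On the joint reading, or if increase is itself a condition, it does not.

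The size cannot be derived from the documents. The fall in power from 0.78 to 0.24, and the percentages for unequal persistence, rest entirely on assumed entry shares, persistence rates and worsening rates.

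Two further inferences are not supported. The primary result is not affected: the hierarchy in SAP 18.3 covers MADRS, CGI-SS and time to treatment failure, and this measure is outside it. Nor is a material effect on time to treatment failure shown. The lack-of-efficacy definition in protocol 16.3.3 and SAP 16.3 uses similar absolute wording, but it operates through the treating physician's determination and the central judgement guided by baseline.

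**What to change.** For the analysis definition of this Fisher measure only:

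1. Keep the threshold and add the reference: a post-baseline C-SSRS ideation score of 4 or more **and** above the patient's own Day 1 score (Visit 2, the randomization baseline, consistent with Table 1 and SAP 20.3). Dropping the threshold and counting any rise would bring in changes such as 1 to 2, which the present rule does not count.
2. State whether hospitalization for emergent suicidality is an alternative or a joint condition, so that a patient hospitalized at an unchanged score is handled by rule.
3. Report persistence at 4 or more on a separate line.

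The sponsor should also check the similar absolute wording in protocol 16.3.3 and SAP 16.3 for consistency with the baseline-guided judgement in protocol 16.8.6 and SAP 20.2.

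The cost is SAP wording and programming; Table 1 already schedules the C-SSRS at Day 1 and at every later treatment visit. The drawback is fewer counted events.

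Two other inconsistencies need reconciling but are not needed for this fix: the Screening recall period (four weeks in SAP 12.1.1, six months in SAP 17.2.2), and entry on items 3 and 4 together (SAP 8) against either or both (inclusion criterion 10).

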16.8.9 Safety Endpoints

Adverse events will be classified by MedDRA. For each study treatment, safety data will be collected and analyzed while on treatment or until treatment-emergent adverse events are resolved. The type, incidence, timing (onset, duration), relationship, and severity of AEs will be reported for treatment-emergent and SAEs. Reasons for withdrawal due to AEs will also be reported. Narratives will be written for every AE classified as serious or associated with attempted suicide or death.

Safety and tolerability will be assessed using two-sided Fisher Exact tests to compare overall adverse event incidence for NRX-101 vs. lurasidone. Mean changes from randomization baseline will be displayed for each serum chemistry and hematology parameter as well as the shift; unpaired t-tests will be used to compare treatments. In addition, paired t-tests will be performed for the changes from randomization baseline for each study treatment group.

Vital signs and ECGs (means and mean changes from baseline will also be evaluated within treatment groups using paired t-tests and between study treatment groups using unpaired t-tests. Percent with abnormal vital signs, heart rate, QRS duration, PR interval, RR interval, QT, and QTcF will be reported. McNemar paired comparison tests will be performed within study treatment groups for the abnormal discordant percent while two-sided Fisher Exact tests will be performed to compare incidences between treatment groups.

Blood draws for chemistries and hematologies will be evaluated within and between study treatment groups. Abnormality rates will be presented relative to established site-specific normal ranges and whether or not the abnormality is clinically significant. McNemar paired comparison tests will be performed within study treatment groups for the abnormal percents while two-sided Fisher Exact tests will be performed to compare incidences between treatment groups.

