Statistical Methods:	All randomized participants will be evaluated for depression (MADRS) suicidality (C-SSRS), and other efficacy endpoints while on the study. Analyses will be conducted under ICH E9 (R1) guidelines. Change from baseline in MADRS total scores through study exit to compare treatments will be analyzed using Mixed Model Repeated Measures analysis (SAS PROC MIXED) with Last Observation Carried Forward (LOCF) containing BPI rating scale (none, any) and evidence of a suicidal event in their lifetime (none, any) as stratification factors. Additional analyses will alternatively rely on multiple imputation to assess the impact of dropouts. The NRX-101 and lurasidone treatment groups will be compared using stratified and unstratified log rank tests, as well as a proportional hazard model for time to relapse.
Sample Size Calculation:	Participants will be randomized in a 1:1 ratio (NRX-101:lurasidone). With 37 participants per group, there is an 80 percent power to detect a mean 8.85-unit advantage for NRX-101 vs lurasidone for the CFB to Day 42, assuming a SD of 13.4 for NRX-101 versus lurasidone at 6 weeks for a two-sided hypothesis test with two-sided 5 percent Type I error. This equates to a 0.66 effect size.
Interim Analysis	Two interim analyses are planned. The first interim analysis (IA) assessing safety will be conducted six weeks after the first 30-35 participants have been followed for 6 weeks and the second IA assessing futility (primary efficacy endpoint) will be performed after the first 45-50 participants have reached 42 days post-randomization. Each interim analysis has a different objective with neither interim analysis spending any Type 1 error. The study will be stopped at the first interim analysis if Serious Adverse Events are deemed statistically significantly more common in the NRX-101 group compared to the lurasidone group in a manner deemed by the DMC to pose a potential danger to human subjects. The study will be stopped at the second IA for futility if the conditional power (CP) is less than 10%. In the event that the study is not stopped for either safety or futility, then enrollment will continue until a total of 74 subjects are randomized. This preserves two-sided p=0.05 for the final analysis.

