## **13. REGULATORY STANDARDS**

The study analyses will be conducted in a GCP environment (ICH E6 and E9 [R1]). All analyses will be pre-specified and finalized prior to database lock. If the methods in this SAP do not agree with the protocol, the methods described in the SAP will govern the analysis.

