### **19.3 Conventions**

Study visit dates will be analyzed using the nominal visit instead of the actual visit date.

Means, mean changes, standard deviations, and ranges will be presented separately for each treatment group. These endpoints will be evaluated using a paired t-test and between study treatment groups using an unpaired t-test at each time; these p-values will be presented as descriptive statistics.

For continuous variables, the mean, standard deviation, minimum, median and maximum will be presented, together with the total number of observations and the number of missing and non-missing values.

For ordinal and categorical variables, absolute and relative frequencies will be reported. Relative frequencies will be based on all observations and reported as percentages. Unless otherwise specified, percentages will be based on the number of participants with data and will not be calculated for missing categories.

Adverse events, medical histories, and concomitant medications will be reported on a patient and an event basis. Percentages will be calculated using the number of participants in the Safety population analysis set as the denominator.

All hypotheses will be tested at 5 percent (final analysis) level of significance using a two-sided test unless otherwise specified.

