## 20. STATISTICAL METHODOLOGY

### 20.1 General Methodology

The Mixed-Effect Model Repeated Measure (MMRM) will be the primary analysis for the primary efficacy endpoint (MADRS change from baseline); an unpaired t-test will be a secondary analysis. The proportional hazard model (PHREG) will be the primary analysis for time to event endpoints (time to remission, time to discontinuation); the unstratified log rank test will be a secondary analysis. The MMRM and PHREG models will all include treatment and the following four baseline covariates:

- sex
- mood stabilizer use
- anti-psychotic use
- evidence of suicide event in their lifetime.

All primary analyses will be in the mITT population as primary and repeated in the Per Protocol population if >5 percent are excluded.

All of the instruments used to measure SSIB or depression constitute serial continuous and ordinal outcomes that will be analyzed using MMRM with LOCF to account for missing data and early discontinuations. The models will include treatment group, study visit, the interaction between study visit and treatment group, the baseline level of the variable being analyzed, and the above four pre-defined baseline stratification factors as fixed effects. The primary endpoint change from baseline MADRS-10 will be analyzed using the MMRM model which will include baseline MADRS; treatment group; study visit; study visit\*treatment; sex, mood stabilizer use, anti-psychotic use, and evidence of suicide event in their lifetime as defined above. An unstructured error structure will be assumed.

SAS PROC MIXED will be used for continuous endpoints.

In addition, supportive analyses will be performed using multiple imputation which will be performed to address any missing data. The method of Little and Rubin will be used. The presentation of the results for the primary efficacy endpoints using the ITT population will be based on the observed data with multiple imputation for missing endpoint data using SAS PROC MI. Missing data will be imputed using MCMC imputation under the assumption of a missing at random using the mITT population. The SAS® procedure PROC MI will be used for the MCMC imputation of 25 complete data sets.

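### Continuous safety measures are compared between arms without baseline adjustment: valid, but less precise than ANCOVA and sensitive to chance baseline imbalance (minor)

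*Protocol*

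**What the plan says.** The two documents specify the same method.

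- **Vital signs and ECG.** Protocol 16.8.9 covers both levels and changes: "Vital signs and ECGs (means and mean changes from baseline will also be evaluated". They are to be "evaluated within treatment groups using paired t-tests and between study treatment groups using unpaired t-tests". SAP 20.5 repeats this.
- **Laboratory.** "Mean changes from randomization baseline will be displayed for each serum chemistry and hematology parameter as well as the shift" (Protocol 16.8.9), and in SAP 20.5 "unpaired t-tests will be used to compare treatments".
- **Which document rules.** SAP 13: "If the methods in this SAP do not agree with the protocol, the methods described in the SAP will govern the analysis". Because SAP 20.5 keeps the protocol's method, this clause changes nothing here.
- **Status of the tests.** SAP 19.3, like Protocol 16.8.3, says of t-tests on means and mean changes that "these p-values will be presented as descriptive statistics".
- **Contrast with the rating scales.** The repeated-measures models in SAP 20.1 include "the baseline level of the variable being analyzed" as a fixed effect. No such term is planned for vital signs, ECG or laboratory values.

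The schedule of assessments (Table 1 in both documents) has vital signs and ECG at Screening and Day 1, and chemistry and hematology at Screening only before dosing. Neither safety section asks for a confidence interval on these between-arm differences.

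**The concern.** A change score subtracts the whole baseline value, as if baseline and follow-up were perfectly correlated. A raw follow-up mean subtracts none of it, as if they were uncorrelated. Most physiological measures lie between the two, so each comparison discards information that the trial has already collected.

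The consequence shows when the arms happen to differ at baseline. Part of the difference in change is then regression to the mean, and part of the difference in raw means is simply the baseline gap carried forward. For vital signs and ECG both comparisons are planned. They respond to the same imbalance in opposite directions, and the plan does not say which to read. With 37 per arm, estimates for measures such as QTcF or creatinine are already wide, so unnecessary noise makes them harder to interpret.

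**Working it through.** **Inputs.** n = 37 per arm, 1:1 (Protocol 16.6.2, SAP 18.2). Assumptions, because the documents give no values: correlation rho between baseline and follow-up from 0.3 to 0.9, the same SD at both times, and all 37 per arm observed. Results are in units of that SD.

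**The plan's own figure.** No precision is stated for safety measures, so the check is on the MADRS sample size. 8.85 / 13.4 = 0.66. A two-sample t-test with 37 per arm has 79.98% power at 0.66, against the stated 80%. The smallest significant effect is 1.993 × sqrt(2/37) = 1.993 × 0.2325 = 0.463, against the stated 0.462. The figure reproduces, and 0.2325 is also the standard error of a chance baseline difference between arms.

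**Formulas.** Per-patient variance is 2(1 − rho) for a change score, 1 for a raw follow-up value and 1 − rho² for ANCOVA. Relative to ANCOVA, the variance ratio is therefore 2/(1 + rho) for changes and 1/(1 − rho²) for raw means. If the arms differ at baseline by b, the expected difference shifts by −(1 − rho)b for changes and by +rho·b for raw means. The last two columns put b = 0.2325.

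| rho | Change: variance ratio | Change: SE excess | Raw mean: variance ratio | Shift, change | Shift, raw mean |
|---|---|---|---|---|---|
| 0.3 | 1.40/0.91 = 1.54 | 24.0% | 1.10 | −0.163 | +0.070 |
| 0.5 | 1.00/0.75 = 1.33 | 15.5% | 1.33 | −0.116 | +0.116 |
| 0.7 | 0.60/0.51 = 1.18 | 8.5% | 1.96 | −0.070 | +0.163 |
| 0.8 | 0.40/0.36 = 1.11 | 5.4% | 2.78 | −0.046 | +0.186 |
| 0.9 | 0.20/0.19 = 1.05 | 2.6% | 5.26 | −0.023 | +0.209 |

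Charging ANCOVA for the extra parameter lowers the change-score ratios slightly, to 1.52, 1.32, 1.16, 1.10 and 1.04.

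**Validity, by simulation** (50,000 trials at each rho, 37 per arm, no true difference, change scores):

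| | rho 0.5 | rho 0.7 |
|---|---|---|
| Mean estimated difference | 0.000 | 0.000 |
| Type I error, all trials | 5.0% | 5.0% |
| Slope of estimate on baseline imbalance | −0.50 | −0.30 |
| Same slope under ANCOVA | about 0 | about 0 |
| Rejection rate when imbalance exceeds 1 SE | 9.1% | 7.7% |

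An imbalance above 1 SE in either direction occurs in about 31.7% of trials. At rho 0.5 the remaining trials must then reject at about (5.0 − 0.317 × 9.1) / 0.683 = 3.1%, which brings the average back to 5%.

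**Illustration in QTcF.** Assume an SD of 18 ms and rho 0.5. The 95% half-width is 1.993 × 18 × 0.2325 = 8.3 ms for change scores, and 8.3 × sqrt(0.75) = 7.2 ms for ANCOVA. A 1-SE imbalance is 18 × 0.2325 = 4.2 ms and shifts the change-score difference by 2.1 ms (2.9 ms at rho 0.3, 1.3 ms at rho 0.7, 0.4 ms at rho 0.9). All of these scale with the SD: from 12 to 24 ms the half-widths run from 5.6 to 11.1 ms for change scores and from 4.8 to 9.6 ms for ANCOVA.

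**The case against.** The strongest reply is that nothing the trial decides rests on these tests. Their p-values are descriptive by convention. The hierarchy in Protocol 16.6.2 and SAP 18.3 holds MADRS, CGI-SS and time to treatment failure, with no continuous safety measure. The interim safety stop rests on serious adverse events. The same safety sections also plan laboratory shifts, abnormality rates and Fisher exact comparisons, so the t-tests are one display among several. For a stable measure with a correlation near 0.9, the change score gives up only about 3% in standard error. In the QTcF illustration a 1-SE imbalance moves the estimate by about a quarter of its half-width. All of this stands, and it sets the importance at minor.

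What it does not answer is that imbalance moves the estimate itself, not only the p-value, and the estimate is what a reader uses. Nor does the point about stable measures help the planned comparisons of raw means, which lose most exactly where the correlation is high.

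A reader might go further and infer that the comparisons are biased, or that their false-positive rate is inflated. The documents do not support this. Allocation is randomized 1:1, and under randomization the change-score t-test is centred on the true difference and rejects at 5%. The 9.1% and 7.7% rates apply only to trials selected for a large imbalance. Nor do the documents support the inference that a stopping decision could be distorted, given what the interim review is based on.

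**Conclusion.** The point holds as one of efficiency and of robustness to the imbalance that happens to occur, and it is minor. The planned unpaired t-tests on laboratory changes, and on vital-sign and ECG means and changes, are valid, but they leave out a covariate that the trial collects and that the plan uses for its rating scales. The cost is a standard error about 24% to 3% larger for changes, and a variance 1.10 to 5.26 times larger for raw means, as rho goes from 0.3 to 0.9. These sizes rest on the assumed correlations, equal SDs and complete data. The true gain will differ by measure and with missing visits, but its direction does not depend on the value of rho in this range.

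**What to change.** In SAP 20.5 and Protocol 16.8.9, replace the between-arm unpaired t-tests for these measures by ANCOVA at each scheduled post-baseline visit, with treatment and the baseline value of the same measure as terms. Report the adjusted difference with its 95% CI. ANCOVA gives the same treatment estimate whether the outcome is the follow-up value or the change, so one estimate replaces the two conflicting ones for vital signs and ECG.

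Name the baseline: the Day 1 pre-dose value for vital signs and ECG, and the Screening value for chemistry and hematology. Both documents refer to a randomization baseline for laboratory values, but the schedule has no Day 1 draw, so that wording needs reconciling in any case.

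Keep the within-arm changes, shifts and abnormality rates as planned. The cost is a few lines of SAP text and one covariate per safety model, with no new data and no effect on sample size or on the primary analysis.
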